#### 3.2.3. Primary Safety Endpoints

The primary safety endpoints will include:

- Frequency of solicited adverse events (AEs)
- Frequency of serious adverse events (SAEs)
- Frequency of AEs of special interest (AESIs)

See [Section 9](#) for additional details on adverse event definitions.

Monitoring post-PMT administration will occur in three phases:

### **3.2.3.1. Post-PMT Administration monitoring: Bedside for 60 Minutes**

Safety endpoints for all routes of administration will include worsened abdominal pain, fever, tachycardia, and hypotension ([Section 3.2.1](#)). Safety endpoints for upper enteral delivery (i.e., PMT-002 or PMT-003) will include evidence of aspiration (including reduced oxygen saturation, tachypnea, or respiratory distress, as defined above).

### **3.2.3.2. Post-PMT Administration or Post-Enrollment monitoring: Daily for 3 Days**

Safety endpoints for all routes of administration will include new ileus, worsened leukocytosis, new/worsened acute kidney injury, new/worsened serum lactate elevation, new/worsened fever, or worsened diarrhea. The definitions of each adverse event are given in [Section 3.2.1](#). The adverse events commonly encountered in prior FMT studies were given in [Table 1](#).

### **3.2.3.3. Post-PMT or Post-Enrollment Administration Follow-Up**

Safety endpoints assessed at the 7-day follow-up and all subsequent follow-ups will include fever, diarrhea, nausea, and vomiting. Safety endpoints assessed at the 30-day, 90-day, and 180-day follow-ups will include evidence of new metabolic disease, including hyperglycemia, thyroid disease, weight gain or loss.

## **4. Study Population and Duration of Participation**

### **4.1. Inclusion Criteria**

1. One or more episodes of CDI with symptoms including bowel movements altered in frequency or consistency from baseline.
2. Stool test positive for *Clostridium difficile* by EIA by FDA-cleared assay within 7 days prior to enrollment.
3. Age  $\geq$  18 years
4. Meets any one of the listed criteria for severe or severe-complicated/fulminant disease (see [Table 2](#) below) within 72 hours of enrollment.
5. Receiving antibiotic treatment for S/SC/F-CDI per current IDSA guidelines.

Enrollment criteria details:

1. Must either meet  $\geq$ 1 criteria in severe category or in severe complicated category to be enrolled.
2. If the subject meets criteria in both categories, stratify to the higher severity category (severe complicated).
3. Detailed enrollment criteria definitions (for [Table 2](#)):
  - a. WBC  $\geq$ 15,000 cells/uL – if any value in the time period meets this definition.
  - b. Hypotension with systolic blood pressure sustained  $<$  90mmHg for three or more hours or requiring vasopressors (epinephrine, norepinephrine, phenylephrine, or vasopressin).

- c. Acute kidney injury – increase in serum creatinine level by  $\geq 50\%$  or new dialysis initiation.
  - i. If a baseline serum creatinine value is not available, acute kidney injury will be defined as a serum creatinine  $>1.5$  mg/dL.
- d. Temperature  $\geq 38.5$  °C or  $<35.6$  °C - one value needed in time period.
- e. Ileus, bowel dilation or megacolon.
  - i. Ileus: If noted in any provider documentation or problem list (search words “ileus”) OR
  - ii. If the words “dilated” “dilation” or “ileus” are noted in a radiology report on intestines/colon, or if “megacolon” noted.
- f. Lactate  $>2.2$  mmol/L - if any value in the time period meets this definition.
- g. SIRS criteria:
  - i. Heart rate  $> 90$  beats per minute
  - ii. Respiratory rate  $> 20$  breaths per minute or  $\text{PaCO}_2 < 32$  mmHg
  - iii. Temperature  $>38^\circ\text{C}$  or  $<36^\circ\text{C}$
  - iv. WBC  $> 12,000$  cells/uL,  $<4,000$  cells/uL, or  $>10\%$  immature (band) forms

Use Table 2 below to decide if the subject meets criteria for enrollment and their stratification category (severe versus severe-complicated).

**Table 2: Enrollment and stratification criteria**

	WBC $\geq 15,000$ cells/uL	Acute kidney injury	Hypotension	Ileus, bowel dilation, or megacolon	Temp $\geq 38.5$ °C or $<35.6$ °C	Use of vasopressors/hypotension	Lactate $>2.2$ mmol/L	$\geq 3$ SIRS criteria
WBC $\geq 15,000$ cells/uL	S	S	SC	SC	SC	SC	SC	SC
Acute kidney injury	S	S	SC	SC	SC	SC	SC	SC
Ileus or abdominal distension	SC	SC	SC	SC	SC	SC	SC	SC
Temp $\geq 38.5$ °C or $<35.6$ °C	SC	SC	SC	SC	SC	SC	SC	SC
Use of vasopressors/hypotension	SC	SC	SC	SC	SC	SC	SC	SC
Lactate $>2.2$ mmol/L	SC	SC	SC	SC	SC	SC	SC	SC
$\geq 3$ SIRS criteria	SC	SC	SC	SC	SC	SC	SC	SC

S = Severe category

SC = Severe-complicated category

WBC = white blood cell count

SIRS = systemic inflammatory response syndrome

#### 4.2. Exclusion Criteria

1. Evidence of colon/small bowel perforation at the time of study screening.
2. Goals of care are directed to comfort rather than curative measures.

3. Moderate (ANC < 1000 cells/uL) or severe (ANC < 500 cells/uL) neutropenia.
4. Known food allergy that could lead to anaphylaxis.
5. Pregnancy
  - a. For subjects of childbearing potential (ages 18 to 55), the subject must have a negative urine pregnancy test within 48 hours of consent and no more than 48 hours prior to first product administration.
6. Receipt of FMT or enrollment in a clinical trial for FMT within the last 3 months.
7. COVID-19 infection, as defined by a positive nucleic acid or antigen test within the prior 14 days and symptoms consistent with COVID-19 infection

#### **4.3. Subject Recruitment**

Potential subjects will be identified by active surveillance for inpatients with positive *C. difficile* EIA stool testing at six participating PennMedicine University of Pennsylvania Health System hospitals (see [Section 4.5](#)). A positive stool EIA test for *C. difficile* will prompt review of the electronic health record to determine whether a potential subject may meet inclusion/exclusion criteria. If a potential subject may meet inclusion/exclusion criteria, the study team will contact the subject's inpatient care team to ascertain whether the care team has any objection to the study team enrolling the potential subject. The potential subject (or their designated medical decision-maker) will be contacted to discuss participation. If the potential subject is eligible and wants to participate, informed consent will be obtained. At this time, subjects of childbearing potential (ages 18 to 55) will have a urine pregnancy test performed. If a urine pregnancy test is not able to be performed or if it is positive, the potential subjects will be excluded. A record of all screened subjects will be maintained to evaluate the frequency of identified exclusions or care-team objections. The study will also be open to patients transferred to a participating hospital who had positive *C. difficile* EIA stool testing at an outside hospital prior to transfer, so long as a record of the positive test can be obtained. Care teams at the participating hospitals may refer such patients for participation.

#### **4.4. Duration of Study Participation**

The subjects will participate in the study for 180 days (+/- 7 days) after the last administration of the PMT product. Study participation will conclude with the 180-day follow-up visit (in-person or by telephone).

#### **4.5. Total Number of Subjects and Sites**

Recruitment will be performed at one site with six participating PennMedicine University of Pennsylvania Health System locations: (1) the Hospital of the University of Pennsylvania (HUP), (2) Penn-Presbyterian Medical Center (PPMC), (3) Pennsylvania Hospital (PAH), (4) Lancaster General Hospital (LGH), (5) Chester County Hospital (CCH), and (6) PennMedicine Princeton Medical Center (PMPMC). Enrollment targets 90 subjects, with 30 randomized to each arm.

#### **4.6. Vulnerable Populations**

Children, fetuses, or neonates are not included in this research study because the gastrointestinal microbiome is significantly different between children and adults. Pregnant women will not be eligible to participate in this study due to unknown risks of FMT in pregnancy. Prisoners will be eligible to participate in this study. Disabled, economically- or educationally-disadvantaged persons will be eligible for enrollment. Vulnerable populations will be protected via the informed

consent process, which ensures that enrolled subjects or subject-surrogates understand study risks and benefits. Vulnerable populations will be protected from coercion because there is no financial benefit to participation in the study.

## 5. Study Intervention

### 5.1. Description

Penn Microbiome Therapy suite of investigational products have been described previously in [Section 1.2](#). The product label will include (1) a unique dose identifier (and barcode), (2) the PMT formulation (PMT-001, PMT-002, or PMT-003), (3) a donor identifier, (4) the date of donation and dose processing, and (5) the expiration date.

### 5.2. Intervention Regimen

This study is a randomized, controlled, open label trial. Subjects will be screened to evaluate if they meet inclusion criteria for severe or severe complicated/fulminant CDI. If eligible, subjects will participate in the informed consent process. Following informed consent, subjects will be randomized to one of three arms: (1) standard of care antibiotics (no intervention), (2) PMT-upper GI administration plus standard of care antibiotics, or (3) PMT-lower GI administration plus standard of care antibiotics. In the intervention arms, subjects will then be eligible to receive up to two additional administrations of PMT (upper or lower GI) at 3-day intervals if they do not meet pre-defined criteria for clinical improvement for 24 hours (see [Section 2.1](#)). If PMT administration is unable to be performed on the scheduled days (3-day intervals), administration within 1 calendar day before or after those days will be permitted. Subjects will be assessed for eligibility for an additional dose on the day of repeat administration. Subjects will be followed until 180 days after their last PMT dose.

During the intervention period, following informed consent and randomization ([Section 3.1.2](#)), subjects in either intervention arm (not the standard of care control arm) will receive single-dose PMT administration, with PMT formulation determined per randomization. Administration of the product is described in [Section 5.7](#) below. Subjects will be eligible to receive up to two additional administrations of PMT (per same randomization) at 3 days and 6 days (+/-1 day) after the initial dose if they fail to meet criteria for clinical improvement ([Section 3.2.1](#)) and as long as they do not have bowel surgery. Antibiotics prescribed as part of routine clinical care for CDI will not be altered by the intervention.

### 5.3. Receipt

The prescribed formulation of the investigational product [PMT-001 (Enema), PMT-002 (Suspension) or PMT-003 (Capsule)] will be packaged on dry ice from the PMT manufacturing facility at the University of Pennsylvania. The time of release from frozen storage will be documented and included in PMT product packaging. PMT products will be delivered by study staff or courier in single doses. Upon receipt of the product by the Investigator, packaging (bags for PMT-001 and PMT-002; capsule containers for PMT-003) will be inspected for integrity, and product will be checked to ensure that it is still frozen and logged in the investigational product accountability log. The investigational product label will also be checked to ensure that the proper product is received, and to ensure that the product has not expired.

#### **5.4. Storage**

Investigational products are transported frozen on dry ice by courier or study staff to the clinical location. Investigational products are transported in containers labelled and maintained at a temperature in accordance with federal and local regulations for the transport of biological products.

At the clinical location, administration of PMT-001 or PMT-002 will be initiated within 180 total minutes of product release from frozen storage. At the clinical site, administration of PMT-003 will be initiated within 120 minutes of product release from frozen storage. The time of release from frozen storage will be included in PMT product packaging ([Section 5.3](#)).

PMT-001 and PMT-002 doses will be thawed at room temperature for 30-60 minutes prior to administration. PMT-003 will remain on dry ice until the time of administration.

Any doses released from frozen storage but not administered within the allotted time (180 minutes for PMT-001 and PMT-002, 120 minutes for PMT-003) after release (e.g., due to delays in transport) will be destroyed. In such cases, eligible subjects will be offered another dose, and the release process will be re-initiated.

#### **5.5. Preparation and Packaging**

Preparation of the three investigational products [PMT-001 (Enema), PMT-002 (Suspension), and PMT-003 (Capsule)] will be performed at the PMT manufacturing facility at the University of Pennsylvania. PMT-001 and PMT-002 are packaged in EVA bags suitable for storage at  $< -70^{\circ}\text{C}$  (target  $-80^{\circ}\text{C}$ ). PMT-003 is encapsulated within three nested gelatin capsules (sizes 00, 0, and 1), then packaged in an HDPE capsule container suitable for storage at  $< -70^{\circ}\text{C}$  (target  $-80^{\circ}\text{C}$ ). The three investigational products will be packaged in single doses.

#### **5.6. Blinding**

Neither subjects nor investigators will be blinded.

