#### **3.1.4. Post-PMT Administration monitoring: Daily for 3 Days after Administration/Enrollment**

The subject will be monitored every calendar day for three days after each PMT administration in order to assess their eligibility for repeat up to 2 additional doses of PMT at 3 days after the first administration and 3 days after a second administration (if given), as well as to assess for adverse events. If the subject continues to meet criteria for severe or severe-complicated disease within the prior 24 hours at 3 days after the initial administration and then 3 days after the second administration (if given), the subject will be eligible for a repeat dose of PMT (same formulation as per initial randomization). If PMT administration is unable to be performed at 3 or 6 days following the first administration, then administration within 1 calendar day before or after those days will be permitted. Assessment for eligibility for an additional dose will be performed on the day of repeat administration. For subjects in the non-PMT arm, monitoring will be performed daily for three days after enrollment for adverse event assessment.

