**Figure 1: Allocation to Interventional Group Flow Diagram**

### 3.2. Study Endpoints

#### 3.2.1. Primary Study Endpoints

The primary outcome is resolution of symptoms associated with S/SC/F-CDI, listed below. The primary outcome will be satisfied when the subject is discharged from the hospital (not to hospice or palliative care) or, while the subject remains hospitalized, when the following criteria are met for 72 hours:

- If radiology study or studies performed, ileus/dilation/megacolon either not noted or noted as resolved (electronic medical record search words: “ileus”, “dilated”, “dilation”, or “megacolon”)
- Ileus/megacolon either noted as resolved by any provider documentation or not noted (electronic medical record search words: “ileus”, “megacolon”)
- WBC < 15,000 cells/uL
- Serum creatinine decreased, unchanged, or increased by  $\leq 0.2$  mg/dL over 72 hours (if not receiving continuous renal replacement therapy (CRRT) or hemodialysis (HD))
- Lactate  $\leq 2.2$  mmol/L (if measured by clinical care team)
- No vasopressors used (including epinephrine, norepinephrine, phenylephrine, or vasopressin)
- Temperature  $< 38.5$  °C and  $\geq 35.6$  °C
- < 8 bowel movements per day and < 600 mL unformed stool (if volume recorded)
- Meeting fewer than 3 systemic inflammatory response syndrome (SIRS) criteria (i.e., no more than two of the following: heart rate > 90 beats per minute; respiratory rate > 20 breaths per minute or PaCO2 < 32 mmHg; temperature > 38°C or < 36°C; WBC > 12,000 cells/uL, < 4,000 cells/uL, or > 10% immature (band) forms)

Discharge to hospice, need for bowel surgery (colectomy, diverting ileostomy), and death will count as failures. Subjects who undergo bowel surgery after initial PMT administration will not be eligible for additional administrations.

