## **7. Study Evaluations and Measurements**

### **7.1. Medical Record Review**

The medical record will be reviewed prior to enrollment, in order to assess eligibility, as outlined above. The medical record will be reviewed at 3-day, 7-day, 30-day, 90-day, and 180-day follow-ups to help ascertain primary and secondary outcomes, as well as adverse events (Sections 3.2 and 9.1.3). HIPAA authorization will be obtained with informed consent.

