### **7.4. Laboratory Evaluations**

No laboratory evaluations will be performed as a part of this study. Laboratory values will be collected from review of the subject's electronic medical record, in order to ascertain outcome data and adverse events, as described above.

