### **7.7. Efficacy Evaluations**

The primary outcome (time to resolution of S/SC/F-CDI symptoms) will be satisfied when the criteria listed in Section 3.2.1 are met for 72 hours or when the subject is discharged from the hospital (not to hospice or palliative care). The criteria will be assessed via electronic medical record review as per Section 3.2.1.

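### No arm-blind or programmed derivation of the primary event date is specified in this open-label trial, although almost every input to that date is a dated record field

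*Combined protocol and SAP*

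**What the plan says.** Section 5.6 (Blinding): "Neither subjects nor investigators will be blinded". On scoring the primary endpoint, section 7.7 says: "The criteria will be assessed via electronic medical record review as per Section 3.2.1". Section 7.1 adds that the record is reviewed at the 3-, 7-, 30-, 90- and 180-day "follow-ups to help ascertain primary and secondary outcomes, as well as adverse events". Both statements leave the reviewer unnamed. Neither these sections nor section 8 provides an arm-blind assessor, an adjudication committee or a programmed derivation.

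Section 3.2.1 gives two routes to the event.

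- Discharge: "The primary outcome will be satisfied when the subject is discharged from the hospital (not to hospice or palliative care) or" the second route applies.
- While still in hospital, nine criteria held for 72 hours. Seven are numeric or drug-use items: WBC, creatinine, lactate, vasopressors, temperature, stool count or volume, and SIRS count. Two are text items, one on radiology reports and one on provider notes. The second reads "Ileus/megacolon either noted as resolved by any provider documentation or not noted". Both come with literal search words.

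Some items count only where a value exists. Lactate applies "if measured by clinical care team", and radiology and stool volume carry similar conditions. Section 7.4 says "No laboratory evaluations will be performed as a part of this study"; values come from routine care. Section 8.5.2 declares a difference at one-sided p below 0.2.

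**The concern.** Where the arm is known to everyone and the event date is read from a chart, a reader who expects FMT to work may, without intending it, date resolution a little earlier in FMT subjects. The analysis is of time to event, the planning durations in 8.4 are only 1 to 7 days, and the threshold is a lenient one-sided 0.2, so a shift of a fraction of a day in one arm can move the result. A positive finding would also be open to the charge of assessor bias.

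Treatment cannot practicably be masked here, but derivation of the event date largely can be. The plan does not use that opportunity.

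**Working it through.** **1. Who scores?** The documents do not say. Three places make it likely that the scorer knows the arm. Table 3 puts the outcomes check at the same follow-ups as the adverse event check. Section 10.3 restricts the stored case report forms to study personnel. Section 6.2.4 judges repeat-dose eligibility with reference to 3.2.1, which can only be done knowing the arm. That is inference. What can be checked is that no separation is written down.

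**2. How much discretion is there?** Nine criteria less seven numeric or drug-use items leaves two text items, and those have search words. Three openings remain:

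- deciding what counts as a note that ileus or megacolon has resolved;
- treating a criterion as met when nothing was measured;
- dating the run. Sections 3.2.1, 7.7 and 8.1 require 72 hours but do not say whether the event is dated at the start or the end, a difference of 72/24 = 3 days.

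**3. The plan's own figures.** Inputs: 90 subjects, 2:1 allocation, an event for everyone, exponential times. Schoenfeld's formula gives power = Φ(√(90 × 1/3 × 2/3) × ln(ratio of durations) − z), with √20 = 4.472.

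| Scenario in 8.4 | Stated | Two-sided 0.2 (z = 1.2816) | One-sided 0.2 (z = 0.8416) |
|---|---|---|---|
| 4 to 2 days | 0.97 | Φ(4.472 × 0.6931 − 1.2816) = 0.965 | 0.988 |
| 7 to 4 days | 0.90 | Φ(4.472 × 0.5596 − 1.2816) = 0.889 | 0.952 |

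The stated powers fit a two-sided test, whereas 8.5.2 is one-sided. That is a separate matter to reconcile. The setting is close enough to use for the error rate.

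**4. Effect of a proportional shift with no true effect.** If every FMT time is scored a fraction s too short, the false-positive rate is Φ(4.472 × (−ln(1 − s)) − 0.8416).

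| Assumed s | One-sided 0.2 | Two-sided 0.2 | One-sided 0.05 |
|---|---|---|---|
| 0 | 0.200 | 0.200 | 0.050 |
| 2% | 0.226 | 0.202 | 0.060 |
| 5% | 0.270 | 0.212 | 0.078 |
| 10% | 0.356 | 0.249 | 0.120 |

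This is an extreme case, because it moves every FMT subject. It shows that the one-sided 0.2 threshold makes the absolute rise larger.

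**5. Shifts in some subjects, allowing for discharge.** Assumptions: no true effect, exponential times with median 4 days, 15% failures kept in the risk set, 60 FMT to 30 control, benefit declared at z > 0.8416, 12,000 simulated trials per cell (standard error about √(0.2 × 0.8/12,000) = 0.004). A discharge date is treated as one a chart reader cannot move.

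| Assumed shift in FMT subjects | No event fixed by discharge | 50% fixed | 80% fixed |
|---|---|---|---|
| none | about 0.20 | about 0.20 | about 0.20 |
| 0.5 day in half | 0.23 | 0.21 | 0.19-0.20 |
| 1 day in a quarter | 0.23 | 0.21 | 0.20 |
| 1 day in half | 0.26 | 0.22-0.23 | 0.20-0.21 |

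The smallest shift tried, half a day in a quarter of FMT subjects, gave 0.21 to 0.22 with no discharge route. Repeat runs of the same cell differ by up to two points (0.220 to 0.241 for half a day in half).

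**6. Equal shift in both arms.** Moving a quarter of subjects in each arm one day earlier (mean 4 or 7 days, no failures) leaves the rate at 0.198 or 0.196. An undefined dating rule applied equally therefore does not inflate the error. It matters only if it is applied differently by arm.

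**The case against.** The case against acting is reasonable.

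- Most criteria are thresholds on recorded values, and the text items are already tied to search words, so a chart reader has little to move. This stands, and it is why the effect is small.
- Discharge alone meets the endpoint and has a fixed date. In a trial of inpatients it may settle many events. This also stands: at an 80% share the calculated effect disappears into simulation error.
- The missing 72-hour dating rule is a gap in definition rather than assessor bias. That is right. It belongs here because it is one of the few places where a reader must choose, and a program forces the choice to be written down.
- The larger route to bias may be the care team, which knows the arm and decides discharge and which tests to order. Arm-blind derivation does not touch that. This stands as a limit on the remedy.

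A reader might infer that the unblinded study team scores the primary event. No section says so, and 5.6 speaks of subjects and investigators, not outcome abstractors. A reader might also infer that present staff would be masked if references to treatment were deleted from the notes. People who enrolled or dosed the same subjects in a 90-subject trial could still recognise them, so that cannot be relied on.

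**Conclusion.** The gap is real but modest. The plan specifies neither arm-blind scoring nor a programmed derivation of the primary event date, and nothing keeps scoring apart from staff who know the arm. The criteria are objective enough for the date to be derived without the arm, and that same objectivity limits how far a reader could shift it.

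The rate of 0.26 at the top of the simulated range should be read as an upper illustration. It assumes that no event is fixed by discharge and that half of FMT subjects are dated a full day early. The discharge share is unknown. The documents give no size or direction for any shift, and a shift against FMT would lower the rate. They therefore do not support saying that the error rate is inflated in this trial, only that an inexpensive protection is missing. This is a worthwhile improvement, not a flaw that undermines the design.

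**What to change.** In 7.7 and 8.1, state the following.

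- The primary event date is derived by one fixed program from exported, dated fields (laboratory values, vital signs, vasopressor use, stool counts, discharge time and destination), with no arm variable in the extract.
- The two text items are taken from the keyword search in 3.2.1, with a rule set in advance for what counts as a record of resolution.
- The program contains an explicit rule for items not measured within the 72-hour run.
- One rule says whether the event is dated at the start or the end of the run, and it is applied identically in all arms.
- The dates are locked before the arm is merged.

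If any text still has to be read by hand, name who reads it and whether they know the arm.

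The cost is a data export and a short program, with no added subjects, visits or procedures. Bias from unblinded care, test ordering and discharge timing remains and should be acknowledged when the result is reported.
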